4.8 Questionnaires

Severe Asthma Questionnaire (SAQ) (Appendix 7)

The new questionnaire will provide a combined assessment of disease and its treatment on the quality of life of patients with severe asthma (13). The scale is based on existing HRQoL

scales but modified for the severe population and provides separate assessments of the effect of asthma symptoms and the effect of asthma medicines. The questionnaire has 16 items assessing experience over the last two weeks and was produced from detailed qualitative research. An additional 3 items are included to assess overall QoL during the last two weeks, and QoL during different months of the year

General Symptom Questionnaire (GSQ) (Appendix 8)

The GSQ is a 65 item questionnaire that was designed to measure the symptoms of patients with fibromyalgia, irritable bowel syndrome and chronic fatigue syndrome (12). The questionnaire assesses the frequency of extra-pulmonary symptoms, such as somatic and psychological symptoms, on a 6 point Likert scale (the value scoring for each response shown in brackets): “Never or almost never” (1), “Less than 3 or 4 times per year” (2), “Every month or so” (3), “Every week or so” (4), “More than once per week” (5) or “Every day” (6). This questionnaire was used to measure the number and frequency of extra-pulmonary symptoms reported by patients. The scale measures frequency of symptoms. This questionnaire be completed by potential participants at baseline to identify those that report 8 or more non-respiratory symptoms per week and are eligible to participate. At subsequent time points, participants will complete the GSQ-A.

General Symptom Questionnaire-A (Appendix 9)

This is an abridged GSQ consisting of 16 non-respiratory symptoms that are associated with asthma severity. It uses the same 6 point Likert scale as the full GSQ.

The Positive and Negative Affect Schedule (PANAS) (Appendix 10)

This questionnaire measures positive and negative affect and consists 20 questions in total, 10 measuring positive affect and 10 measuring negative affect. Participants respond to each question by using a 5 point scale where 1 indicates “not at all” and 5 indicates “very much”.

Asthma Control Questionnaire (Asthma Control Questionnaire) (Appendix 11)

This questionnaire contains 7 items and takes into consideration FEV1% predicted and daily use of rescue bronchodilator. Patients respond to 7 items concerning their symptom severity on a 0-6 scale (0 = no impairment, 6 = maximum impairment) (14). The questionnaire asks patients to assess their symptoms over the last week.

Note: the included questionnaires are available and validated in the majority of European languages and many non-European ones. However, if a participant requires a translation of a questionnaire that is not available, they will not be asked to complete the particular questionnaire.

Post course questionnaires

Global Rating of Change Questionnaire – Phase one (Appendix 12)

This scale will be used by participants to indicate how much better they feel since commencing a BR. The 11-point scale ranges from -5 (a great deal worse) to 5 (A great deal better) (15). The time scale is between before the start of treatment and the current assessment.

All questionnaires are presented in paper and pencil format, to be self-completed by the patient but with support if needed.

Friends and Family Test (FFT) (Appendix 13)

This is a one question questionnaire used throughout the NHS to assess patient's thoughts on a health service they regularly use. The question we will use in the FFT asks "We would like you to think about your recent experience of our Body Reprogramming. How likely are you to recommend Body Reprogramming to friends and family if they needed a similar service?

" Participants will respond on a 5 point scale from "Extremely Unlikely" to "Extremely Likely".

Questionnaire completion

Data on the number and percentage of questionnaires collected at the two time points will be recorded. This data will inform participants' willingness to complete the above questionnaires.

Post-trial focus groups or interview

Focus groups will consist of 3-6 participants and moderated by one of the members of the research team with qualitative research experience (LC, MH, JL). Two focus groups will be

conducted in total, and will explore the experience of participants after participating in a four-week trial of BR.

Each focus group will last for at most 2 hours, be recorded and transcribed verbatim. The focus groups will be conducted in a non-clinical setting near to the recruiting site (RD&E) or remotely via Zoom. Participants will have their transport costs reimbursed and provided with refreshments during the discussion. They will not be paid for taking part.

If a participant declines to take part in a focus group, they will be given the option to participate in a one to one interview. Some people find group interactions challenging and the interview option will be included to make sure we do not miss out on participant feedback when possible.

Overall the direction of conversation during the focus groups or interviews will be led by the participants in order to investigate their experiences of BR. Any problems that are brought to the attention of the research team during the trial will be discussed during these conversations.

4.9 Description of Data analyses

For quantitative data

This is a feasibility study and so not powered for statistical testing. This section describes the data to be collected which will inform the design of future studies.

- The number and percentage of participants that are invited, attended and completed the BR course will be reported.
- All outcome measures will be summarised using means and standard deviations or median (range, IQR) for continuous outcomes (as appropriate), and frequencies and proportions for categorical outcomes.
- The mean difference in all recorded scores (pre and post-trial at listed time points post-trial) will be estimated and in addition using an analysis of covariance of the baseline value of the score as well as disease severity as a covariate in the model.
- The number and percentage with complete data will be reported. The missing value guidance provided for questionnaires will be used. If no guidance is provided values

will be imputed for an individual if 20% or fewer items are missing. If greater than 20% of items are missing in the questionnaire then the questionnaire score will be treated as missing and excluded from the analysis.

- The number of adverse events (AE) and serious adverse events (SAE) will be tabulated also by the number of patients reporting an event. No dictionary for coding adverse events will be used. Events will be recoded using terms of the clinical investigators choosing.
- A full statistical analysis plan will be drawn up and agreed by the CI and study team prior to the final data extraction.

For qualitative data

Once transcribed, the audio recordings from the focus groups or one to one interviews will be analysed for recurring themes. The information gained from this phase will be used to make changes to practical aspects of the BR course, e.g. length of meetings or number of weeks, as well as adapt the narrative of the course for patients with severe asthma if required.

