Body Reprogramming (BR) is a non-drug, multi-component intervention originally developed in Plymouth for fibromyalgia patients (see www.bodyreprogramming.org) and provided to patients through the NHS with direct referral from a GP in Devon and Cornwall. BR is applicable to any patients whose polysymptomatic presentation cannot be explained by current disease models (10). The aim of BR is to improve general health and well-being by evidence-based lifestyle change. The unique feature of BR is a theoretical model that personalises lifestyle advice to the particular patient and provides patients with a narrative that explains how and why the changes can produce benefit.

The theoretical model proposes that symptoms result from a network of biological symptom causing mechanisms (11). The extra-pulmonary symptoms of severe asthma can be explained by inflammatory mediators being part of this network that include, but are not limited to, non-specific pro-inflammatory cytokines (8). Patients are provided with a simplified version of the theory based on an analogy of 'hardware' and 'software' faults in a computer (9).

3. Study Design

This is an unblended observational study, single-site feasibility study in two phases:

Phase 1 Proof of concept.

The aim of this study is to assess the feasibility and acceptability of BR, whilst optimising the intervention for people with severe asthma.

Phase 2 Biologic priming feasibility study.

Patients expected to start a biologic treatment for their severe asthma will be invited to take part in a BR course.

Participating sites include:

- Royal Devon and Exeter Hospital NHS Foundation Trust, Exeter, UK (RD&E)

4.0 Phase 1: Proof of Concept, Four-Week Trial of BR and Post-Trial Focus Groups or Interviews

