5.4 Exclusion criteria

- Unable or unwilling to take part.
- Participated in phase 1 of the study
- In the opinion of the patient's treating physician, the patient has another condition which is significantly impairs their ability to take part in BR.

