5.7 Description of Statistical Methods

The statistical methods will be the same as that for phase one. The researchers will examine whether there is any trends indicating differences in outcome between phase one and phase two

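### Does the ANCOVA planned within a single treated group need changing because it can only repeat the mean paired change?

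*Combined protocol and SAP*

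**What the plan says.** Section 4.9 of the combined protocol and SAP first sets out the simple estimate: "The mean difference in all recorded scores (pre and post-trial at listed time points post-trial) will be estimated". The same sentence then adds a model-based estimate, "using an analysis of covariance of the baseline value of the score as well as disease severity as a covariate". It names no group term, does not say which output of the model will be reported, and does not define disease severity. Section 4.7 lists several clinical variables that could serve: spirometry, exacerbations, steroid burden and healthcare use.

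Section 3 describes a "single-site feasibility study in two phases" with no control arm. The two delivery groups in section 4.6 both receive the intervention, so they are not comparison arms. For Phase 2, section 5.7 states "The statistical methods will be the same as that for phase one" and adds: "The researchers will examine whether there is any trends indicating differences in outcome between phase one and phase two". Section 5.4 excludes from Phase 2 anyone who "Participated in phase 1 of the study", so the phases contain different people.

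On purpose, section 4.9 states: "This section describes the data to be collected which will inform the design of future studies". It disclaims power for testing, and section 5.9 marks the significance level as not applicable. It also says: "A full statistical analysis plan will be drawn up and agreed by the CI and study team prior to the final data extraction".

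**The concern.** Analysis of covariance is normally used to compare groups after allowing for baseline. Within one phase there is nothing to compare, so the natural output is an adjusted mean, and at the average covariate values that mean is the unadjusted one. A report showing a mean change beside an ANCOVA mean change could lead a reader to think an adjusted analysis had confirmed a raw one, when the two agree by construction.

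Two further worries follow. If a confidence interval were taken from the model, it would usually be narrower than the paired interval without a real gain in precision for the population mean change. And the quantities a later randomised trial would want (SD of change, pre-post correlation, residual SD) are not listed by name, although section 4.9 says its data are meant to feed into later study design.

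**Working it through.** **Inputs from the documents.** Two time points, first and last week (4.7); one treated group per phase (3, 4.6); 12-14 recruited per phase (4.10, 5.8); 10% withdrawal and at least 10 completers in Phase 1 (4.10). The documents give no SD or pre-post correlation r, so r = 0.3 to 0.9 is an assumed range, with normal scores and equal pre and post SDs.

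**The plan's own figure.** 12 × 0.9 = 10.8 and 14 × 0.9 = 12.6, so at least 10 completers is reproduced. This counts course completers; the number of usable score pairs could be lower.

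**The identity.** Let x be the first-week score, y the last-week score, d = y − x, and s severity. Fit d = a + b(x − x̄) + c(s − s̄) + e by least squares. The residuals sum to zero, so the estimate of a is d̄, the mean paired change. With y as the response, the estimate of a is ȳ, and ȳ − x̄ = d̄ again. In 5,000 simulated data sets at each of n = 10, 12 and 14, the largest gap for either form was below 1e-15. It follows that the choice of severity variable cannot move this estimate, provided the variable is recorded for everyone analysed.

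**When the number differs.**
- Severity as two categories, weighted equally instead of as observed: for an assumed 4-versus-8 split and a 0.5 SD effect, the shift is 0.5 × (1/2 − 4/12) = 0.08 SD.
- Severity missing for some people: the model gives the paired mean in fewer participants. With 2 of 12 missing at random and r = 0.6, the SD of the difference is √(2(1 − 0.6)) × √(1/10 − 1/12) = 0.894 × 0.129 = 0.12 score SD.
- Read one baseline SD from the mean: the fitted change moves by (1 − r) score SD, that is 0.7, 0.5, 0.3 and 0.1 at r = 0.3, 0.5, 0.7 and 0.9.
- A model pooling the two phases: the adjusted phase contrast is not the raw difference in changes. With 12 per phase and r = 0.5, the gap between them has an SD of about 0.22 score SD, so ANCOVA does add something there.

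**If an interval were taken from the model** (the plan states none). The large-sample ratio of ANCOVA to paired standard error is √((1 − r²)/(2 − 2r)). Coverage of the population mean change by a nominal 95% interval was simulated with 20,000 data sets per setting, n = 10 to 14, severity unrelated to change:

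| r | SE ratio | ANCOVA coverage | Paired coverage |
|---|---|---|---|
| 0.3 | 0.81 | about 90% | about 95% |
| 0.5 | 0.87 | about 92% | about 95% |
| 0.7 | 0.92 | 93-94% | about 95% |
| 0.9 | 0.97 | 94-95% | about 95% |

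**What the planning inputs could deliver.** Limits for the two-covariate residual SD are √(df/χ²) with df = n − 3: 0.66 to 2.04 times the estimate at n = 10 and 0.71 to 1.70 at n = 14. For the SD of change, df = n − 1: 0.69 to 1.83 and 0.72 to 1.61. By Fisher's z with standard error 1/√(n − 3), an observed r of 0.7 has a 95% interval of 0.13 to 0.92 with 10 pairs and 0.27 to 0.90 with 14.

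**The case for a change.** The best case for a change is that it costs only wording and that the full SAP is still to be written. The sentence in 4.9 does attach the ANCOVA to the estimate of change, so reading it as a second estimate is fair. The agreement is then automatic, an interval from the model would be too short for this estimand, and an undefined severity covariate leaves room for a choice made after the data are seen. The score SDs that 4.9 plans do not give the SD of change without the correlation.

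Much of this is true as statistics. What stands is a drafting preference: the SAP would read better if it took the mean change and any interval from the paired analysis, listed the number of pairs, the SD of change and the correlation, and said what the ANCOVA is for.

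What does not stand is that following the current text would lead anyone astray. The paired estimate is planned in its own right. The interval problem concerns an output the plan does not state. A paired difference is ordinarily reported with its SD, and the criticised model is itself the source of the residual SD and baseline slope. Exact redundancy also holds for only one reading of a sentence that does not say where the model is evaluated.

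**Conclusion.** No change to the plan is needed. At the observed covariate means, with categories weighted as observed and the same participants analysed, the ANCOVA point estimate equals the planned mean paired change, a difference of zero. An additional analysis that returns the same number does no harm to the result, and removing it would alter no estimate or conclusion. Under other readings it answers another question, and one of them, the look across phases in 5.7, is a use where it would contribute.

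The primary objectives in 4.2 and 5.2 concern willingness, experience, acceptability and process, and none depends on this model. Nothing is tested or powered on it. The missing details (the severity variable, the reported quantity, the named planning outputs) are of the kind a study team fills when writing the full SAP that 4.9 already requires. Even when named, the planning inputs would be too imprecise at 10 to 14 pairs to fix a later sample size by themselves.

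The identity assumes least squares and complete severity data. The coverage and precision figures assume normal scores, and the coverage figures also assume equal SDs, the stated values of r and no severity effect on change; none of these values comes from the documents.

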4.7 Data collection time points

Participants will be asked to complete a series of questionnaires (see section 4.8) when they attend the Body Reprogramming course during the first and last week. These will be posted to the participant's home address by a research nurse, completed, and returned to the patients' clinic using a FREEPOST envelope.

At the end of the course, participants will be asked to complete a course feedback form.

If participants have not returned the questionnaire within two weeks the questionnaire pack will be sent out again. If a further two weeks pass without the return of questionnaires a researcher will contact participant by phone and ask if they need assistance.

Patients will be asked to text or email the course co-ordinator if they are unable to attend a course date for any reason. Experience shows that health and other problems can prevent patients from attending, so attendance monitoring requires this form of data.

Demographic data

The following demographic and clinical information will be collected from the participants' clinical records at baseline by a researcher:

Patient demographics:

- Age
- Sex
- Ethnicity
- Smoking status

Clinical data

Most recent spirometry (in the last 6 months),

Major co-morbidities (respiratory and non-respiratory as identified by the patient's clinician)

- Current Drug treatment
- Asthma exacerbations requiring systemic steroids in the last 12 months,
- Cumulative steroid burden in the last 12 months,
- Healthcare utilisation: hospital admissions / Emergency Department attendances in the last 12 months.

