5.6 Data collection Method

Questionnaire collection time points are the same as for phase one:

- The first and last week.

Demographic and clinical information will be the same as for phase one.

The outcome measures will be the same as for phase one.

The Global Rating of Change Questionnaire (GRCQ) (Appendix 16)

In this phase of the study the GRCQ will be used by participants to indicate how much better they feel since commencing a **BR and a biologic treatment**. The 11-point scale ranges from -5 (a great deal worse) to 5 (A great deal better) [17].

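### Section 4.9 promises AE and SAE counts, but no supplied section of either phase systematically elicits or extracts events after baseline, so the table could not be read as an event rate

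*Combined protocol and SAP*

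**What the plan says.** The analysis section (4.9) commits to a safety table: "The number of adverse events (AE) and serious adverse events (SAE) will be tabulated also by the number of patients reporting an event". It also sets a naming rule, with no coding dictionary: "Events will be recoded using terms of the clinical investigators choosing".

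The collection sections describe the following.

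- **Questionnaires (4.7).** Participants complete them "when they attend the Body Reprogramming course during the first and last week". The packs go by post, with a re-send after two weeks and a phone call after two more.
- **Feedback (4.7).** "At the end of the course, participants will be asked to complete a course feedback form". Its content is not described.
- **Clinical records (4.7).** Demographic and "clinical information will be collected from the participants' clinical records at baseline by a researcher". The items include "Asthma exacerbations requiring systemic steroids in the last 12 months", and admissions and ED attendances over the same look-back.
- **Phase 2 (5.6).** Time points and clinical data are those of Phase 1, and so are the outcomes: "The outcome measures will be the same as for phase one".

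AE, SAE, AR and SAR are spelled out in the glossary. The supplied text gives no definition, collection window, form or responsible person for them. AEs are not among the outcome measures in the Study Summary, nor among the data types listed in 6.7.

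**The concern.** A table needs a source. Here the output is specified, down to the choice of terms, but the input is not. If events are recorded only when someone happens to mention them, the count depends on who misses a session, who speaks up and who joins a focus group. A low count could then mean few events or little asking, and the reader could not tell which.

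Participants have severe asthma, so some exacerbations and healthcare contacts during the study would be unsurprising whatever the effect of the course. Phase 2 is meant to inform a possible randomised trial (5.1). Its planners would want to know how often such events occur over a course of this length and whether they can be captured. The table as planned answers neither question.

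**Working it through.** **Plan's own figure.** The plan gives no number for adverse events. The only derived figure nearby is the completers in 4.10: 12 × 0.90 = 10.8 and 14 × 0.90 = 12.6, which agrees with the stated minimum of 10. The point does not depend on it.

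**Step 1: trace each collection step to the table.**

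| Step | Where | Could it feed an AE count? |
|---|---|---|
| SAQ, GSQ/GSQ-A, PANAS, ACQ | 4.8 | They score quality of life, symptom frequency, affect and control. A score can worsen, but none is described as recording an event, its date or its seriousness |
| GRCQ, Friends and Family Test | 4.8, 5.6 | Overall change and willingness to recommend; no events |
| Course feedback form | 4.7 | Content not visible; not described as an AE form |
| Record extraction | 4.7, 5.6 | History before the course; no repeat is described |
| Absence messages | 4.7 | Only from those who miss a session; kept for attendance |
| Session report-backs and questions | 4.6 | About practice at home; speaking is optional (1.3) |
| Reminder calls | 4.7 | Only to non-returners; about help with questionnaires |
| Focus groups or interviews | 4.8 | Participant-led; cover problems already raised |
| Distress contingency | 6.1 | Offers a clinician; no recording step |

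The first four rows are planned for every participant, and none is described as recording post-baseline events. The other five could surface an event, but none is linked to an AE record.

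**Step 2: direction of the error.** Events that are not asked about are lost, and nothing in the plan adds spurious ones, so the count is biased towards zero. Section 5.10 pushes the same way. A participant who becomes ineligible after a change in health or diagnosis has their data removed, and such participants may be the ones with events.

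**Step 3: exposure.** No start or end date for AE recording is given, so patients in the table have no common period at risk.

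**Step 4: illustration of size.** The inputs below are assumptions, not figures from the documents. Let n be patients over both phases (12 + 12 = 24 to 14 + 14 = 28), p the true share with at least one event, and c the fraction of those patients captured, independently of one another. Expected patients in the table = n·p·c. Chance of an empty table = (1 − p·c)^n.

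| p | c | Expected patients, n = 24 to 28 | Chance of an empty table, n = 24 to 28 |
|---|---|---|---|
| 0.10 | 1.00 | 2.4 to 2.8 | 0.080 to 0.052 |
| 0.10 | 0.25 | 0.60 to 0.70 | 0.545 to 0.492 |
| 0.10 | 0.10 | 0.24 to 0.28 | 0.786 to 0.755 |
| 0.30 | 1.00 | 7.2 to 8.4 | 0.000 |
| 0.30 | 0.25 | 1.8 to 2.1 | 0.154 to 0.113 |
| 0.30 | 0.10 | 0.72 to 0.84 | 0.481 to 0.426 |
| 0.50 | 1.00 | 12 to 14 | 0.000 |
| 0.50 | 0.25 | 3.0 to 3.5 | 0.041 to 0.024 |
| 0.50 | 0.10 | 1.2 to 1.4 | 0.292 to 0.238 |

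For example, with p = 0.30 and c = 0.10: 0.97^24 = 0.481 and 0.97^28 = 0.426. With c unknown, an empty or sparse table says little about p.

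**The case against.** The strongest reply is that this is a small, uncontrolled feasibility study of an educational course. Section 6.1 judges the potential for harm minimal, safety is not an objective, and no feasibility conclusion rests on the AE table. The wording in 4.9 about patients reporting events also fits spontaneous reporting, and there are several contacts after baseline through which reports could come. Part of the absence cannot be verified: the feedback form and most appendices are not in the supplied text, 6.7 does not restrict routine clinic data to baseline, and 4.9 defers detail to a full SAP.

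Much of this stands, and it limits the point. A reader might infer that nothing is collected and that the table would be empty whatever happened. The documents do not support that, because the incidental routes could surface some events. A reader might also infer that the team plans to present the table as evidence of safety in a trial application. No section says so: 5.1 ties the future trial to acceptability and the performance of outcome measures.

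What does not stand is that the gap is harmless or will settle itself. Having chosen to report AEs, the plan needs a way to obtain them. A later SAP can define the denominator and period, and could even request a record look-up, but it cannot recover patient-reported events that nobody asked about.

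**Conclusion.** The point holds as a gap between a promised output and the described collection. Followed as written, the AE and SAE table would be incomplete, biased towards zero and without a common exposure period, and could not be read as an event rate in either phase. It is worth repairing before data collection; it does not undermine the feasibility outcomes.

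The size of the shortfall cannot be derived from the documents, because neither the true event share nor the capture fraction is given; the table above is an illustration only. A reader might be tempted to measure the defect by the upper limit for zero events, 1 − 0.05^(1/12) = 0.221 and 1 − 0.05^(1/14) = 0.193. Those figures assume complete collection and reflect sample size alone. They would be the same after the repair, so they do not measure this defect.

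The conclusion assumes that the unseen feedback form and appendices contain no adverse-event item. No section body refers to one.

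**What to change.** If the feedback form or an appendix already elicits adverse events, a cross-reference in 4.7 and 5.6 meets items (b) and, if records are covered, (c). Otherwise amend 4.7 and 5.6 as follows.

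- (a) Set one AE/SAE window by the same rule for everyone: from consent to a set date tied to the scheduled last session, not to return of the pack. Reminders can delay return by weeks, and non-returners would have no end date. Consent dates will differ, so report the length of the window.
- (b) Add one open adverse-event question to the last-week pack, and log the health reasons given for missed sessions.
- (c) Repeat the baseline look-up of exacerbations, admissions and ED attendances once for that window, including for non-returners.
- (d) Tabulate against all consented participants, showing separately those who attended at least one session, so that events in people who never start are not lost.
- (e) Reconcile 5.10 with 4.9 so that events in participants who become ineligible after a change in health stay in the AE table.

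The cost is one added question, one repeat look-up per patient for 12–14 patients per phase, and wording; the downside is slightly more research-nurse time. One limit remains: for participants who do not return the last-week pack, events outside the record items would still be found only by chance.
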